4.3. Participation Period

Participants are expected to participate in the study for 60 days after study start. The product may be used after each onset of indigestion and heartburn episode, but not exceeding three times per day. Participants will be discontinued from the study 60 days after Study Start or after three recorded episodes of indigestion and heartburn. Study start is defined as the day the participant recorded received receipt of the test product on the start form in the platform.

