2.2.3. Minimization of Risks

Research participants will be carefully screened to meet enrollment criteria. Participants meeting exclusion criteria will not be enrolled. The study participant informed consent will be presented with clear description of the study requirements and opportunity to have questions answered before enrollment. Once an event occurs, review of symptoms will be ascertained at onset, 15, 30, and 60 minutes. Reporting of adverse events will be reviewed routinely and in accordance with regulatory guidelines (21CFR, GCP) by the Principal Investigator. Participants with occurrence of worsening symptoms or adverse

events will be advised to stop taking the test product, may seek medical attention, and exit the study.

3. Study Objectives

The purpose of the present study is to evaluate 1) the impact of the test product on symptoms of occasional indigestion and heartburn in 200 adult participants who suffer from occasional indigestion and heartburn and 2) the subjective experience of these participants related to general health, indigestion and heartburn symptoms, and personal experience with the test product.

This will be evaluated based on the primary and secondary endpoints. These endpoints, the analysis populations, and their respective measures are described below. Further details on the methods for measuring the outcomes can be found in the Study Outcome Measures and Analysis Plan sections.

Primary Endpoint:

The primary endpoint has two components, reduction in indigestion severity and reduction in heartburn severity. Participants will be asked to rate each symptom (bloating, early fullness during a meal, pain or discomfort in the upper abdomen, burning in the upper abdomen, pain/burning in the center of your chest, nausea, vomiting, and burping) on a 4-point scale at 4 time points: prior to taking the test product, 15, 30, and 60 minutes after taking the test product. The improvement in symptoms from baseline will be evaluated on a pairwise basis separately for each component and each time point. P-values will be computed for the improvement. Given that indigestion can impact an individual's quality of life, the primary endpoint was chosen to see the test product's effects on symptoms. [1, 9, 12]

Secondary Endpoint:

Secondary endpoints will be analyzed to evaluate safety and patient satisfaction with relief of symptoms. These include:

- The time to other intervention will be analyzed.

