6.1. Study Procedures

- Candidates will review information about the study and complete a screening form.
- During the screening process, the candidate will be asked questions regarding their symptoms and medical history to ensure that they meet the requirements to participate in this study.
 Potential participants will also be asked questions to ensure that they do not meet any of the exclusion criteria and meet all of the inclusion criteria.
- After successful screening (participant does not meet any exclusion criteria), participants will review and sign study informed consent form.
- Upon verification of signed informed consent, participant will be enrolled into the study.
- At time of enrollment, participant will be given access to the HIPAA compliant study portal.
 - The study portal provides access to study information, signed informed consent form, instructions for test product use, frequently asked questions, study surveys, symptom diary, and data collection tools.
- Participant shall complete baseline assessments upon access to the portal.
 - Baseline assessment will include questions regarding the participants' demographics, medications, detailed information regarding their indigestion/heartburn including treatment.
- To ensure that baseline assessments are completed before test product is used by the
 participant, study materials and study welcome package will be shipped to the participant once
 the clinical study manager/clinical ops coordinator confirms that the baseline assessment has
 been completed.
- The welcome package will include an information sheet that will outline instructions for their participation in the trial, the test product, and paper forms of the documents (paper form of

- study documents will be provided for real time data collection, in the event that the participant cannot log into the study portal to input data).
- Once the participant receives the test product, the participant will log into the study portal to acknowledge the receipt of the test product.
- Study start date will be the reported date of receipt of test product.
- Participant will be sent weekly email reminders that remind them of their participation in the study.
- At the onset of the indigestion and heartburn episode, the participant will start a Symptom Diary and complete a 4-point Likert scale for each of the symptoms they are experiencing.
 - Onset is defined as the point in time the participant takes the test product for relief of symptoms.

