- After completing the surveys, the participant will take the test product. The participant will take
 2 capsules per indigestion and heartburn episode. With a max of 6 capsules per day. (If
 participant takes 6 capsules in 1 day this will be defined as 3 indigestion and heartburn episodes
 and the participant will be exited from the study).
- After taking the test product, the participant will complete a 4-point Likert scale assessment for each symptom at 15 minutes, 30 minutes, and 1 hour after taking the test product.
- When the participants symptoms have resolved , the participant will complete the symptom diary.
- If the participant takes any other medication outside of the test product, the participant will record this on the symptom diary.
 - The participant is allowed to take alternative medications or supplements AFTER 1 hour from taking the test product.
- After taking the test product, the participant will be instructed to fill out an Adverse Event form for any side-effects experienced.
- After the first episode of indigestion and heartburn, the participant will be asked to complete the same process for another 2 episodes within the 60-day study time frame; however, these are not required.
- If the participant completes the required assessments for a total of 3 episodes of indigestion and heartburn, they will be prompted, by email, to exit the study.
- If the participant only completes the required assessments for the required 1 episode of indigestion and heartburn, the participant will be prompted, by email, to complete the study exit form and will be exited from the study on day 60 (60 days from the day of receipt of the test product).
- Neither the sponsor nor Hawthorne Effect Inc. will not collect any unused test product.
- Upon receipt of study exit survey and review of completed study forms, participant will receive an Amazon gift card of \$25 via email.

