6.2. Study Schedule of Activities

Assessments	Screening	Consent	Before Receipt of Test Product	Test Product Received	Event 1	15 Minutes After Event Start	30 Minutes After Event Start	60 Minutes After Event Start
Study Window								
Screening Survey	X							
Consent		X						
Baseline Survey			X					
Demographics			X					
Acknowledgement of receipt of test product				X				
Symptom Diary					X			X
4-point Likert Scale					X	X	X	X
Test Product Consumed					X			
Medications & Supplements			X					
AE Assessment					X	X	X	X
Study Exit Survey								

Assessments	Event 2	15 Minutes After Event Start	30 Minutes After Event Start	60 Minutes After Event Start	Event 3	15 Minutes After Event Start	30 Minutes After Event Start	60 Minutes After Event Start	Study Exit
Study Window									
Screening Survey									
Consent									
Baseline Survey									
Demographics									
Acknowledgement of Receipt of Test Product									
Symptom Diary	X			X	X			X	
4-point Likert Scale	X	X	X	X	X	X	X	X	
Test Product Consumed	X				X				
Medications & Supplements									
AE Assessment	X	X	X	X	X	X	X	X	X
Study Exit Survey									X

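### Exit is triggered by the third episode or by day 60, not by time since the last dose, so adverse event observation after dosing is unequal and can be very short; the exit assessment has no stated timing or form.

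*Combined protocol and SAP*

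**What the plan says.** Section 4.3 gives two ways for participation to end: "Participants will be discontinued from the study 60 days after Study Start or after three recorded episodes of indigestion and heartburn". Section 6.1 sets the clock: "Study start date will be the reported date of receipt of test product". Day 60 is thus counted from delivery, not from any dose.

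For those who complete three episodes, section 6.1 says "they will be prompted, by email, to exit the study", with no interval given. Rapid use is handled the same way: if a "participant takes 6 capsules in 1 day this will be defined as 3 indigestion and heartburn episodes", that person is exited.

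AEs are collected in several places:

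- **Section 6.2.** The row "AE Assessment" is marked at the start of each event, at 15 and 30 minutes, at "60 Minutes After Event Start", and again at Study Exit. The Study Exit Survey is a separate row.
- **Section 6.1.** Participants are told to complete an AE form for side effects after taking the product. No time limit is attached.
- **Appendix E.** The diary asks about side effects in the part completed once symptoms have resolved.
- **Appendix G.** The AE form covers type of event, description, time after dosing, self-treatment and medical care.
- **Appendix F.** The six numbered exit items cover overall experience, perceived help, recommendation, coping, free comment and avoidance of other medication. None concerns side effects.

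Section 2.2.3 adds that participants with worsening symptoms or adverse "events will be advised to stop taking the test product, may seek medical attention, and exit the study". Section 3 gives safety as one purpose of the secondary endpoints, and sections 3 and 7.1 plan a summary of AEs.

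**The concern.** The only scheduled AE assessment later than 60 minutes after an event is the one at exit, and exit is driven by episode count or by a calendar date. The more quickly a participant uses the supply, the sooner that assessment can follow the last dose. Someone with one early episode stays under observation for weeks. A plain proportion of participants with an AE would mix these windows.

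Two further gaps bear on the exit assessment. The plan does not say which form carries it. A participant who stops because of an AE may leave at that point, and no form asks whether the event resolved. If the exit check falls soon after the last dose, or is not asked at all, the study loses its one scheduled chance to record later effects.

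**Working it through.** The plan gives no figure for observation time, so there is none to reproduce on this point. Its one computed design figure, 97 treated participants, is not in dispute. It reproduces with a paired t-test, mean change 0.5, SD 1.5 and an assumed two-sided 5% level (power at 97 = 0.901).

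**Step 1: limits that follow from the text.** Let *d* be the day of the last dose, counted from receipt.

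- Third dose taken: observation after the last dose = 60 minutes of scheduled assessments + delay in completing the diary and exit survey. The minimum is about 1 hour.
- Fewer than three doses: observation = 60 − *d* days. A single dose on day 1 gives 60 − 1 = 59 days; a last dose on day 59 gives 60 − 59 = 1 day; a last dose on day 60 leaves only the rest of that day.

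**Step 2: how soon three episodes can occur.** Appendix D offers a frequency category of 2–3 times a week. Three episodes then take 3 ÷ (3/7) = 7 days to 3 ÷ (2/7) = 10.5 days. The exit prompt would come roughly 60 − 10.5 = 49.5 to 60 − 7 = 53 days before day 60.

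**Step 3: illustration across frequencies.** The documents give no distribution of episode frequency, so the rates below are assumptions spanning the Appendix D categories. The simulation used 400,000 participants per rate, a constant episode rate, every episode treated, and exit at the third dose or day 60. Delay in returning forms is set to zero. All columns refer to treated participants.

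| Assumed rate | Reach 3 episodes | Mean days, last dose to exit | Mean days, those with <3 episodes | Of those with <3, under 7 days |
|---|---|---|---|---|
| Daily | 100% | 0.0 | – | – |
| 2.5 per week | 100% | 0.0 | – | – |
| Weekly | 99% | 0.2 | 21.8 | 20% |
| 3 per month | 94% | 1.4 | 22.6 | 19% |
| Monthly | 37% | 15.7 | 25.0 | 17% |
| 4 per year | 6% | 25.9 | 27.6 | 14% |

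Under these assumptions three-dose users have about 0 days after the last dose, by construction of the exit rule. Treated users with fewer episodes average about 22 to 28 days, though 14 to 20% of them have under a week because day 60 is fixed. Earlier doses are watched for longer: mean time from first dose to exit runs from 2.0 days (daily) to 32.3 days (4 per year).

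**Step 4: the exit assessment.** Section 6.2 requires an AE assessment at exit. Section 6.1 says when the exit e-mail goes out but not how long after the last dose the assessment should fall. Appendix F cannot record an AE except by chance in free text. Appendix G could be used, but no section assigns it to exit. The 30-day contact in section 6.5 does not fill the gap, since it applies to participants who have supplied no event information.

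**The case against.** A reader might infer that the plan collects no AEs at exit. The documents do not support that. Section 6.2 marks the assessment, in a row separate from the survey, and Appendix G opens with a side-effect question that has no time limit. What is missing is its timing and a named form.

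A reader might also infer that observation always stops within hours. It need not. The AE form in section 6.1 is open-ended, the diary question follows symptom resolution, and exit depends on an e-mail and a returned survey with no stated deadline. One hour is a minimum, although paying the gift card after the exit survey favors prompt return.

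Three stronger inferences also fail:

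- **That AE rates are biased low and later effects are in fact missed.** The documents hold no data on delayed effects. Sections 2.2.1 and 6.4.1 tie the listed events to doses above recommended use, and full use is six capsules against two for one episode, a difference of four.
- **That event outcomes are unknown.** Sections 6.4 and 6.4.2 provide for review and assessment of each AE by the investigator, and Appendix G asks about treatment and requests hospital papers. Only an explicit resolution item is lacking. Section 2.2.3 can be read as permitting exit, and it does not say that review of a reported event then ends.
- **That amenorrhea shows a week is needed.** A week would not reliably detect it either.

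The secondary analyses are called hypothesis generating, and no comparison of AE rates between participants is planned. That limits the consequence. None of this supplies an observation period after the last dose, and the unequal windows follow from carrying out the exit rules as written.

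**Conclusion.** The point stands in a limited form. The exit rules ignore time since the last dose, so post-dose AE observation can range from about an hour plus form-return delay to about 60 days, and it tends to be shortest for those who use all three doses. The exit AE assessment exists in the schedule but has no stated interval after dosing and no named form, and no form asks about resolution.

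The limits of the range come from the protocol text. The averages in the table rest on assumed episode rates, treatment of every episode and immediate exit, so they show direction only. Later effects may be under-ascertained and AE summaries would cover unequal windows; how much this matters cannot be judged from the documents. It does not affect the primary endpoint. It is an inexpensive improvement that should be made, because safety is a stated purpose of the study.

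**What to change.** Leave the limits on product use as they are and separate the end of dosing from the end of safety observation.

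1. State one AE observation interval after the last dose for all treated participants, including those who stopped for an AE. The sponsor should choose and justify its length; 7 days is only an example.
2. Send the exit prompt at the end of that interval. For participants with fewer than three episodes, whose last dose is known only in retrospect, use day 60 or the end of the interval, whichever is later.
3. At that contact, administer Appendix G or add one item to Appendix F asking about any new or worsened health problem since the first dose. Either way, ask whether it has resolved.
4. Reconcile sections 2.2.3, 4.3, 6.1 and 6.2 and Appendix F on when and how exit AEs are collected.
5. In the SAP, summarize AEs over the common interval after the last dose, and list later events separately. Time from first dose to exit will still differ between participants and should be reported.

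The cost is one form item or reuse of an existing form, and a changed trigger for an e-mail already planned. The drawbacks are a short delay to exit and the gift card, and some participants running slightly past day 60.

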4.4. Data Collection

All data in the present study will be self-reported by the participant and collected via their online portal (Hawthorne Effect Study Visit Management System (HE VMS)). Participants will be asked to take the test product according to the instructions for use, complete study surveys and respond to study reminders during the course of the study. The instructions for use and study forms can be found in the appendix. (*Appendices B, D, E, F, G*)

5. Study Population

5.1. Selection of the Study Population

The study population will consist of at least 200 participants who suffer from symptoms of indigestion and heartburn. The participants will otherwise be in good health.

The target sample size for this study is initially 200 participants, with a desired sample of 97 treated participants. This is described in detail in the Statistical Considerations section.

At such time as 180 participants have been enrolled, the available data will be analyzed using a constant hazard model to determine if it seems realistic that the desired number of 97 treated participants will be met by the end of follow-up. If the expected number of treated participants is less than 97, the target sample size will be increased as needed, considering both the desire for 97treated participants and the timelines of the trial sponsor. The actual outcomes of treated

participants will not be considered in this analysis, merely whether or not enrolled participants have reported starting using the test product.

Enrollment will be stopped once the target number of participants has been enrolled, no further participants will be offered a place in the trial once the target sample size criteria has been met. All participants who have already been offered places, but who have not yet consented, will be allowed to participate as long as they have signed the study consent within 15 days and the total number of participants does not exceed 125% of the target (either 200 or the recomputed target if recomputation has been performed.)

In order to ensure an age and sex distribution that is reasonably representative of the US population, enrollment may be stopped early in some age and sex groups.

Target population for this study are candidates who suffer from symptoms of occasional indigestion and heartburn.

Participants will be enrolled from across the United States. No participants will be enrolled outside of the United States. It is expected that the geographical distribution of the participants enrolled in the study will correlate with the geographical distribution of the general population across the United States.

Participants will be recruited via digital advertisements and social media.

After clicking on an advertisement, potential participants will then be directed to a website where they will complete a screening questionnaire (See *Appendix C*). The screening questionnaire will automatically qualify or disqualify them for study participation. If the participant qualifies, they will be provided an informed consent. Upon completion of the informed consent they will be deemed enrolled in the study.

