7.1. Study Outcomes Measures

Analysis populations:

The *intent to treat* (ITT) population consists of all participants who are consented, report the onset of indigestion and heartburn, and have taken the study medication at least once. The primary analysis will be in the ITT population.

Primary Endpoint:

The primary endpoint has two components, reduction in indigestion severity and reduction in heartburn severity. Participants will be asked to rate each symptom (bloating, early fullness during a meal, pain or discomfort in the upper abdomen, burning in the upper abdomen, pain/burning in the center of your chest, nausea, vomiting, burping) on a 4-point Likert scale at 4 time points: prior to taking the test product, 15, 30, and 60 minutes after taking the test product. The improvement in symptoms from baseline will be evaluated on a pairwise basis separately for each component and each time point. P-values will be computed for the improvement.

There is no control group for the primary analysis.

Secondary Endpoints:

Secondary endpoints will be gathered on the subjective experience of these participants related to general health, personal experience with the test product. The secondary endpoints will be self-reported by the participant on their online portal. There will be a questionnaire related to general health and the subjective experience of the participant administered at baseline and at study exit.

The purpose of the secondary analyses is to investigate the association between various baseline and other measurements and outcomes. These secondary analyses are considered hypothesis generating, and the descriptions are somewhat informal. The trial data may suggest secondary analyses not described here.

Secondary endpoints:

- The time to other intervention will be analyzed.
- A longitudinal analysis will be performed for participants who report on more than one incident of heartburn or indigestion.
- Adverse events will be summarized.
- An additional data presentation will consist of results from both Treatment and Control
 in similar studies appearing in the literature. There will be no formal statistical
 comparison of results from this study and historical studies.
- The Net Promoter Score will be summarized and compared against outcomes.
- Comparison against normal behavior will use the paired sample t-test.

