7.2. Sample Size Considerations

Based on information from a variety of studies a highly pessimistic assumption is that there would be a mean improvement of 0.5 with a standard deviation of 1.5. (These values refer to the 4-point scale.) Based on these assumptions, a sample size of 97 participants would result in a 90% power to detect an improvement using the paired-sample t-test. If data from multiple incidents per participant are useful, the power to detect an improvement would increase. The final sample size of 200 participants has been chosen to allow for various contingencies, including uncertainties about compliance in this self-reported trial, and the fact that some participants may not experience heartburn or indigestion during the trial period.

It should be emphasized that these assumptions are for sample size purposes only. Trial analysis will use the data as collected.

As discussed above, the number 200 may be increased based on observed data concerning the number of participants with indigestion and heartburn. The actual outcomes of treated participants will not be considered in this analysis, merely whether or not enrolled participants have reported starting using the test product. The method of reevaluating the sample size will be described in the Statistical Analysis Plan.

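### The sample-size check at 180 enrolled compares 97 with projected product starters, but 97 is the number of paired scores needed for 90% power

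*Combined protocol and SAP*

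**What the plan says.** Section 7.2 takes a mean improvement of 0.5 with SD 1.5 and concludes that "a sample size of 97 participants would result in a 90% power to detect an improvement using the paired-sample t-test". It sets enrolment at 200 to allow for contingencies. Two are named: uncertain compliance with self-reporting, and "the fact that some participants may not experience heartburn or indigestion during the trial period".

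Section 5.1 re-uses 97 as the desired number of treated participants. It plans a check at the 180th enrolment: "the available data will be analyzed using a constant hazard model to determine if it seems realistic that the desired number of 97 treated" people can be attained. If the expected number is below 97, the target is raised, with sponsor timelines also considered. What is counted is "merely whether or not enrolled participants have reported starting using the test product". People already offered places may still join if they consent in time and "the total number of participants does not exceed 125% of the target".

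The primary analysis is in an ITT population that "consists of all participants who are consented, report the onset of indigestion and heartburn, and have taken the study medication at least once". Section 7.1 adds: "The improvement in symptoms from baseline will be evaluated on a pairwise basis separately for each component and each time point". After the first episode, participants are asked to "complete the same process for another 2 episodes within the 60-day study time frame; however, these are not required" (section 6.1). Section 7.2 leaves the re-evaluation method to a SAP that section 7.3 says is still to be prepared.

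**The concern.** The same number is used for two different things. In section 7.2 it is the number of within-person differences entering a t-test. In section 5.1 it is the number of people who have taken a capsule. Someone who takes the product but enters no 15-, 30- or 60-minute score counts toward the 97, belongs to the ITT population, and contributes nothing to the paired test. Section 7.2 recognises imperfect compliance when it sets 200, but the trigger in section 5.1 is a bare 97 and carries none of that allowance. A later episode could supply the missing pair, but later episodes are optional, and the text does not say whether one may stand in for the first in the primary test.

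The second question is the projection. A single constant hazard gives every participant who has not yet started the same daily chance of starting. The baseline form (Appendix D) allows episode frequencies from a few times a year to every day, and section 7.2 expects some participants to have no episode. Measured from receipt, frequent sufferers start early and leave the risk set, so the pooled rate falls with time and a constant rate projects too many later starters.

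At stake is the one planned decision on whether to enrol more than 200.

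**Working it through.** **1. Reproduce 97.** Inputs from section 7.2: mean 0.5, SD 1.5, power 90%, paired t-test. Alpha is not stated; two-sided 0.05 is assumed because it returns the protocol's figure. Power is P(|T| > t with probability 0.975 on n-1 df), where T is noncentral t with noncentrality (0.5/1.5)√n. At n = 97 the noncentrality is 0.3333 × 9.849 = 3.283 and power is 90.1%. At n = 96 power is 89.8%. So 97 is the minimum number of complete pairs, with no margin for loss.

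**2. Pairs left if the check is met at exactly 97 starters.** The documents give no missing-score rate, so the loss m is assumed. With only the first episode usable, pairs = 97(1-m) rounded down, and starters needed = 97/(1-m) rounded up.

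| m | pairs | power | starters needed for 97 pairs |
|---|---|---|---|
| 5% | 92 | 88.6% | 103 |
| 10% | 87 | 86.7% | 108 |
| 20% | 77 | 82.3% | 122 |

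Suppose any episode may supply the pair, half of starters report one further episode, and losses are independent. The share with a pair is then 1 - (m + m²)/2. For m = 10% this is 0.945, giving 91 pairs (88%). For m = 20% it is 0.88, giving 85 pairs (86%). If every starter reports a second episode, m = 20% gives 97 × 0.96 = 93 pairs (89%).

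**3. Projection.** The decision threshold is 97/200 = 48.5% first use. Assumed inputs: episode rates of 4, 12, 36, 52, 130 and 365 per year in equal shares for the six Appendix D categories; a further share who never use the product; 7-day shipping; and even accrual over 120 days (the 6-month study duration less 60 days). The 180th participant enrols on day 108. Those enrolled by day 108 - 7 - 60 = 41 have completed 60 days: 41/120 × 200 = 68.

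True starters: the chance of no episode in 60 days, averaged over the six rates, is (0.518 + 0.139 + 0.003 + 0 + 0 + 0)/6 = 0.110. Expected starters are 200 × 0.890 = 178 with no never-users, and 89 with 50%.

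Constant hazard with 50% never-users, in expected values: 67.8 starters in 4,567 person-days at risk give 67.8/4,567 = 0.0148 per day. Applying 1 - exp(-0.0148 × days remaining) to the 112.2 not yet started adds 29.1. The last 20 to enrol add 20 × (1 - exp(-60 × 0.0148)) = 11.8. The total is 67.8 + 29.1 + 11.8 = 108.7, or 109, against a true 89.

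Simulation at exactly 200 enrolled gives the share of trials where the check passes but true starters fall below 97:

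| never-users | projected / true | constant hazard | Kaplan-Meier |
|---|---|---|---|
| 0% | 188 / 178 | 0% | 0% |
| 40% | 128 / 107 | 8% | 2% |
| 45% | 118 / 98 | 41% | 7% |
| 50% | 109 / 89 | 75% | 7% |
| 55% | 99 / 80 | 55% | 2% |

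With a mostly infrequent mix (60% a few times a year) and no never-users, the projection is 138 against 131 and no decision is wrong. With 30% never-users it is 100 against 92, and 42% of trials are wrongly reassured (11% with Kaplan-Meier).

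The start of the clock is not stated. Counting from enrolment reduces the bias (103 against 89 at 50% never-users) and can reverse it: 87 against 96 if all have episodes a few times a year, none are never-users and shipping takes 14 days.

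**4. Which fault matters more.** Assume 40% never-users and 15% of episodes without a pair, with only the first episode counting. The mean is 90 pairs (88% power). The check passes with fewer than 97 pairs in 81% of trials as written, 66% with Kaplan-Meier on starters, and 8% with Kaplan-Meier on pairs. If any episode counts, the figures are 14%, 6% and 3%. When only the first episode counts, most of the gain comes from changing the count.

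**The case against.** The case against has real weight, mostly on the projection. Spread in episode frequency alone produced no wrong decision in either mix tried. The harm needs an assumed 20-60% of consenting sufferers who never use the product, whereas section 7.2 says only that some may have no episode. The protocol also works against non-use, with weekly reminders, a coordinator contact at 30 days and a gift card after form review. If 30% of never-users began after the day-30 contact (assumed), the 50% case would give 114 starters and under 1% false reassurance. Enrolment is at least 200 and may overrun; at 220 or 250 enrolled, the 75% falls to 32% or 1%. All of this stands, and it makes the projection a secondary point.

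On the count, section 7.2 chose 200 partly for compliance and notes that data from several incidents per person would raise power. The planning values are called highly pessimistic: with an assumed SD of 1.2, 77 pairs still give 95% power. These soften the loss but do not repair the trigger, which tests 97 with no such allowance.

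It may be said that the SAP will settle the method. It could, for instance by fitting constant hazards within frequency groups, which the wording does not rule out. But section 5.1 already names the model, the count and the threshold, and a SAP that follows it inherits the count.

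A reader might also infer that the final report will claim 90% power. No section says so; section 7.2 states that its assumptions serve sample size only.

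**Conclusion.** The mismatch of count holds on the text alone: 97 is a number of pairs, and the check compares it with starters. Its size rests on an assumed missing-pair rate. At 10-20%, a check met at exactly 97 starters leaves 87-77 pairs and 87-82% power, or 91-85 pairs and 88-86% if half of starters supply a usable repeat episode. That is a loss of a few points of power on cautious planning values.

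The projection point holds in direction for a clock started at receipt. It affects the decision only when true first use is near or below 48.5% of 200, which requires a substantial share of never-users that the documents do not give.

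Two stronger readings are tempting and are not supported. One is that the trial is underpowered: if uptake and diary completion are good, 200 enrolled yields well over 97 pairs. The other is that the constant hazard makes the check fail in general: with no never-users it over-projects harmlessly. This is a point to consider in the SAP, held with medium confidence.

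**What to change.** In section 5.1 and the SAP:

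- **Count pairs.** At the check, count participants with an onset score and at least one scheduled post-dose score. Show the count for each component and time point, blind to the values. State whether a later episode may supply the pair. Compare the smallest relevant projected count with 97.
- **Project from receipt.** Run the clock from product receipt, which section 6.1 already defines as study start. Use Kaplan-Meier to day 60, giving each participant without an event the probability 1 - S(60)/S(current follow-up). A constant hazard within baseline-frequency groups that allows for never-users would also serve. Report either at least alongside the constant-hazard figure. On the timeline above, about 68 of 180 would have reached day 60, so S(60) can be estimated.
- **Restate power.** If the target is not increased, give the power for the expected number of pairs.

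The cost is a few lines of text and code, using diary data already collected and the R survival package named in section 7.3. The check stays blind to outcomes. The downside is a less favourable projection and some unneeded increases when first use is near the threshold. In the simulations these were about 10% of trials (9-11% at 40-45% never-users), against 0% under the present rule.
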